4.4.1.2.5 Duration

Duration is derived from the start and stop dates of the unsolicited non-serious AE provided in the clinical database:

- stop date of unsolicited non-serious AE - start date of unsolicited non-serious AE + 1.

The duration should be considered as missing only if one or both of the start and stop dates of the unsolicited non-serious AE is missing or partially missing.

4.4.1.3 SAEs

4.4.1.3.1 Last Vaccination

The last vaccination before any SAE is defined as the study vaccination at V01.

4.4.1.3.2 Time of Onset

Time of onset will be computed using the same methodology than for unsolicited non-serious AEs described in Section 4.4.1.2.4.

SAEs will be analyzed throughout the study using the following periods:

- During the study (i.e., all SAEs occurred during the study)
- Within 30 days after vaccination

An SAE with missing time of onset will be considered to have occurred just after the vaccination indicated by the visit number, so will be included in these tables.

Note: SAEs that occurred before vaccination (negative time of onset) will not be included in analysis, but will be listed separately.

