4.3.2.3.4 Serious Adverse Events

Information on SAEs will be collected and assessed throughout the trial, from inclusion until 180 days (+14 days) after vaccination.

Any SAE occurring at any time during the trial will be reported by the Investigator through the electronic data capture (EDC) system and according to the completion guidelines provided by the Sponsor. All information concerning the SAE is to be reported, either as part of the initial reporting or during follow-up reporting if relevant information became available later (e.g., outcome, medical history, results of investigations, copy of hospitalization reports). The Investigator will assess the causal relationship between the SAE and the investigational product as either “Not related” or “Related”, as described in Section 4.3.2.3.7.

See protocol for further details on SAE reporting.

4.3.2.3.5 [REDACTED]

Not applicable.

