4.4.1.2.4 Time of Onset

Time of onset is derived from the start date of the unsolicited non-serious AE provided in the clinical database and the date of last vaccination:

- start date of the unsolicited non-serious AEs – date of previous vaccination

The time of onset should be considered as missing only if one or both of the dates are missing or partially missing.

The unsolicited non-serious AEs will be analyzed “Within 30 days”, which corresponds to AEs with a time of onset between 0 and 30 days after vaccination or missing. An AE with missing time of onset will be considered to have occurred just after the vaccination indicated by the visit number, so will be included in these tables.

Note: Unsolicited non-serious AEs that occurred before vaccination (negative time of onset) or with a time of onset higher than defined above will not be included in analysis, but will be listed separately.

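### Read as written, the SAP puts an SAE with a partly missing start date in the 30-day table even when its recorded month and year prove onset after Day 30

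*SAP*

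**What the plan says.** **Collection and periods.** SAP 4.3.2.3.4: "Information on SAEs will be collected and assessed throughout the trial, from inclusion until 180 days (+14 days) after vaccination". SAP 4.4.1.3.2 reports SAEs for two periods, the whole study and "Within 30 days after vaccination".

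**Onset.** For SAEs, 4.4.1.3.2 states: "Time of onset will be computed using the same methodology than for unsolicited non-serious AEs described in Section 4.4.1.2.4". That section, 4.4.1.2.4, subtracts the vaccination date from the start date and adds: "The time of onset should be considered as missing only if one or both of the dates are missing or partially missing".

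**Missing onset.** Under 4.4.1.3.2: "An SAE with missing time of onset will be considered to have occurred just after the vaccination indicated by the visit number", and the event enters the tables just listed. SAP 4.4.1.2.4 has the parallel rule for unsolicited non-serious AEs and counts missing onset as part of its 30-day period. Both sections send events with negative onset to a separate listing. SAP 4.4.1.2.4 does the same for non-serious AEs with onset after day 30.

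**Which vaccination.** SAP 4.4.1.3.1: "The last vaccination before any SAE is defined as the study vaccination at V01".

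**Start dates.** SAP 5.3.1.5 does not impute partial start dates for unsolicited AEs. It includes those with missing onset by the visit at which they were collected.

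**The concern.** A conservative rule for missing dates is sound when the data leave real doubt about whether an event fell near vaccination. Here the rule also reaches events for which there is no doubt. A recorded month and year can prove that onset lay outside D0 to D30, and the derivation discards that information.

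The two SAE periods separate events close to vaccination from those arising over six months of follow-up. Moving a provably late event into the 30-day table blurs that separation, and for late SAEs the rule can only add to the 30-day count. SAE counts in such a window are often small, so a single misplaced event can be visible.

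The rule also weakens the SAP's own provision for pre-vaccination events. An event dated only to an earlier month has missing onset, not negative onset, so it is included in the analysis and escapes the separate listing.

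**Working it through.** The documents give no figure that depends on this rule, so there is none to reproduce. The check traces the rule and then uses calendar arithmetic.

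**1. The chain**

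| Step | Source | Result for an SAE dated only to month and year |
|---|---|---|
| Method for onset | SAP 4.4.1.3.2 | Follows 4.4.1.2.4 |
| Partial date | SAP 4.4.1.2.4 | Onset is missing |
| Missing onset | SAP 4.4.1.3.2 | Placed just after vaccination, in both tables |
| Vaccination | SAP 4.4.1.3.1 | Always Visit 1, so the visit number separates nothing |
| Follow-up | SAP 4.3.2.3.4 | True onset may be as late as D180 (+14 days) |

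No section uses the known month or year.

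**2. A late SAE.** Vaccination on 10 October 2016 lies inside the planned vaccination period of 15 July to 30 December 2016 (Protocol 5.1.5). Suppose an SAE is dated March 2017. Days from 10 October to 1 March = 21 + 30 + 31 + 31 + 28 + 1 = 142. The last compatible day is 142 + 30 = 172, before that subject's D180 (8 April 2017). Every compatible date is after day 30, yet the rule gives a 30-day SAE.

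**3. All months, for vaccination on 15 July 2016**

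| Known month | Compatible onset days | Can it be D0 to D30? |
|---|---|---|
| July 2016 | −14 to 16 | Yes |
| August | 17 to 47 | Yes |
| September | 48 to 77 | No |
| October | 78 to 108 | No |
| November | 109 to 138 | No |
| December | 139 to 169 | No |
| January 2017 | 170 to 200 | No |

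**4. How often the month alone is decisive.** Assume vaccination dates are uniform over the planned period and onset is uniform over follow-up. Then 75% (to D180) to 77% (to D194) of all onset days fall in a month wholly after day 30. That is 90% to 91% of the onset days later than day 30. For the other 9% to 10% the month leaves doubt, and conservative inclusion is reasonable.

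**5. A pre-vaccination event.** For vaccination on 10 October 2016, an AE dated September 2016 has compatible onset days from −39 (1 September) to −10 (30 September). All are negative, yet onset counts as missing and the AE is included.

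**6. Size, on assumed rates only.** The documents give no SAE rate and no rate of partial dates. Assume SAE rates of 0.2% by D30 and 1.0% by D180, and a missing day for 5% to 10% of later SAEs.

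| | MenACYW (2700) | Menactra (600) |
|---|---|---|
| SAEs by D30 | 2700 × 0.002 = 5.4 | 600 × 0.002 = 1.2 |
| Later SAEs | 2700 × 0.008 = 21.6 | 600 × 0.008 = 4.8 |
| 5% to 10% of later SAEs | 1.08 to 2.16 | 0.24 to 0.48 |
| Relative to 30-day count | 20% to 40% | 20% to 40% |

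The percentage is the late-to-early ratio (0.8/0.2 = 4) times the share lacking a day. If only 90% of those are provably late (step 4), it becomes 18% to 36%. It scales with the assumed ratio: at half the ratio it is 9% to 18%, at double 36% to 72%.

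**The case against.** **SAP 5.3.1.5 may reach SAEs.** A reader might infer that nothing qualifies the SAE rule and that every partly dated late SAE is bound to be misplaced. The documents do not settle that. The safety definitions in SAP 4.3.2.1 describe unsolicited non-serious AEs as the unsolicited AEs that remain once SAEs are excluded, so unsolicited AEs can include SAEs. SAP 5.3.1.5 speaks of unsolicited AEs without restricting them to non-serious ones, and uses the visit of collection. On that reading, an SAE first collected at the 6-month contact need not enter the 30-day table. This stands as an ambiguity. It does not remove the problem, because 4.4.1.3.2 on its face says otherwise and neither section uses the known month.

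**Partial SAE dates should be rare.** SAEs are reported within 24 hours and updated as information arrives (Protocol 10.1, 10.2). Investigators must seek supporting records (Section 10) and explain missing data (11.1). SAE data are reconciled before release (11.2). Subjects are asked to report SAEs at once and are given a memory aid (5.1.3). This stands. That partial dates cluster at the 6-month call is plausible, but the documents do not say so.

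**The rule is conservative and the same in every group.** It overcounts near-vaccination SAEs, in keeping with the treatment of missing causality as related (SAP 5.3.1.2). Investigators are blinded (Protocol 6.4). The illustration gives the same percentage in both vaccine arms, so it offers no ground for inferring a between-arm bias.

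**Little depends on the table.** Safety is descriptive, with no hypothesis tested (SAP 5.1.3.1), and partial dates will be visible in listings (5.3.1).

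**The pre-vaccination case is marginal.** Pre-existing conditions are not AEs unless they worsen, and the diary is handed out after vaccination. It remains an inconsistency with the SAP's own listing rule.

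**Conclusion.** The concern holds for the rule as written. SAP 4.4.1.3.2 with 4.4.1.2.4 assigns partly dated SAEs to the 30-day table even when the recorded month and year exclude that window, and it includes unsolicited AEs dated only to a pre-vaccination month. SAP 5.3.1.5 may imply another handling, so two programmers could produce different 30-day tables from the same data.

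The reach is narrow: the descriptive 30-day SAE table and the unsolicited AE tables. Late SAEs belong in the whole-study count in any case, so that count is unaffected by them. No primary or secondary conclusion depends on it.

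A reader might take the 20% to 40% in the illustration as a forecast. It is not: it rests wholly on assumed rates. Nor does it predict a misplaced event in the Menactra group, where the same assumptions give fewer than half an event. The true number is unknown and probably small. The reason to act is that the rule contradicts recorded data and is easily corrected.

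**What to change.** In SAP 4.4.1.3.2 and 4.4.1.2.4, use whatever part of the start date is known:

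- If at least one compatible calendar date lies in D0 to D30, count the event as within 30 days.
- If every compatible date is after D30, count an SAE only in the whole-study period, and list a non-serious AE separately, as the SAP already does for late onset.
- If every compatible date is before vaccination, list the event separately.
- If the date is wholly missing, keep the present conservative rule.

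Align 5.3.1.5 with this and state whether it covers SAEs. SAP 4.4.1.4 borrows the calculation methods of 4.4.1.2 for MAAEs, so check its wording at the same time.

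The cost is a few lines of SAP text and derivation code, with no new data. Ambiguous events are still counted conservatively; only events proved to lie outside the window move.

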4.4.1.3.3 Duration

Duration will be computed using the same methodology than for unsolicited non-serious AEs described in Section 4.4.1.2.5.

4.4.1.4 Medically-Attended Adverse Event (MAAE)

MAAEs will be collected as unsolicited AEs in the diary card as part of all unsolicited AEs from D0 to the D30 (+14 days). Unsolicited AEs that have action taken categories 2 or 3 will be summarized and presented as MAAEs between D0 and D30. MAAEs that occur from D30 to D180 (+14 days) will be recorded as such in the MA. Calculation methods are the same as unsolicited non-serious AEs as described in Section 4.4.1.2.

4.4.1.5 Other Safety Endpoints

4.4.1.5.1 Pregnancy

This information will be listed as collected. No derivation or imputation will be done.

4.4.1.5.2 Action Taken

This information will be summarized as collected, including missing observations. No derivation or imputation will be done.

4.4.1.5.3 Seriousness

This information will be summarized as collected. No derivation or imputation will be done.

4.4.1.5.4 Outcome

This information will be summarized as collected. No derivation or imputation will be done.

4.4.1.5.5 Causality

This information will be summarized as collected. Missing causality (relationship) will be handled as described in Section 5.3.1.2.

4.4.1.5.6 AEs Leading to Study Discontinuation

A flag is available in the clinical database for all AEs in order to identify AEs leading to discontinuation.

In general, the items that are counted are:

- Disposition table: A subject who has, on the termination form, the reason for early termination “Serious Adverse Event” or “Other adverse event” is checked.
- Safety overview table: A subject who has either the reason for early termination “Serious Adverse Event” or “Other adverse event” checked or lists an AE on an AE page (solicited, unsolicited, or SAE) that has “Reaction Leading to Termination” or “Event Leading to Termination” or “Serious Adverse Event Leading to Termination” checked on the termination form, that is at least Grade 1 and is within the time period indicated.
- System Organ Class/Preferred Term (SOC/PT) table: An event (solicited, unsolicited, or SAE) that has “Reaction Leading to Termination” or “Event Leading to Termination” or “Serious Adverse Event Leading to Termination” checked that is at least Grade 1 and is within the time period indicated.

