4.3.2.2 Safety Endpoints

The observational endpoints for the evaluation of safety are:

- Occurrence, nature (Medical Dictionary for Regulatory Activities [MedDRA] preferred term), duration, intensity, and relationship to vaccination of any unsolicited systemic AEs reported in the 30 minutes after vaccination.
- Occurrence, time of onset, number of days of occurrence, intensity, action taken, and whether the reaction led to early termination from the study, of solicited (prelisted in the subject's diary card and electronic case report form [CRF]) injection site reactions occurring up to 7 days after vaccination.
- Occurrence, time of onset, number of days of occurrence, intensity, action taken, and whether the reaction led to early termination from the study, of solicited (prelisted in the subject's diary card and CRF) systemic reactions occurring up to 7 days after vaccination.
- Occurrence, nature (MedDRA preferred term), time of onset, duration, intensity, action taken, relationship to vaccination (for systemic AEs only), and whether the event led to early termination from the study, of unsolicited AEs up to Visit 2 after vaccination.

^a All injection site AEs are considered to be related to vaccination and are therefore all *injection site reactions*.

- Occurrence, nature (MedDRA preferred term), time of onset, duration, seriousness criteria, relationship to vaccination, outcome, and whether the SAE led to early termination from the study, of SAEs throughout the trial.
- Occurrence, nature (MedDRA preferred term), time of onset, duration, seriousness, relationship to vaccination, and outcome for MAAEs from Visit 2 to the 6-month follow-up contact. MAAEs will be collected as unsolicited AEs up to Visit 2.

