4.4.1.2 Unsolicited Non-serious AEs

4.4.1.2.1 Presence

An observation will be considered an event if it has at least a verbatim term and is not a Grade 0 intensity event. Grade 0 events should be included in the listing “Unsolicited non-serious adverse events not included in the safety analysis.”

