5.3.1.4 Intensity

For solicited reactions, missing intensities will be handled as described in Section 4.4.1.1.1. For unsolicited non-serious AEs, missing intensities will remain missing and will not be imputed.

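### The grade condition in SAP 4.4.1.5.6 can leave ungraded SAEs and ungraded non-serious AEs out of the SOC/PT table of events leading to discontinuation

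*SAP*

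**What the plan says.** SAP 4.4.1.5.6 introduces its list as what is counted in general, and then gives three rules.

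- The disposition rule begins "Disposition table: A subject who has, on the termination form, the reason for early termination" and relies on the termination form recording an SAE or another AE as the reason. It has no grade condition.
- The overview rule begins "Safety overview table: A subject who has either the reason for early termination" and accepts either that reason or an AE flagged as leading to termination. The grade and time conditions read as attached to the flagged AE.
- The SOC/PT rule begins "An event (solicited, unsolicited, or SAE) that has" and then requires the flag to be "checked that is at least Grade 1 and is within the time period indicated". The termination reason plays no part.

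Three other provisions bear on this:

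- The SAE endpoint in SAP 4.3.2.2 covers, among other attributes, "seriousness criteria, relationship to vaccination, outcome, and whether the SAE led to early termination from the study, of SAEs throughout the trial". Intensity is not among them.
- SAP 5.3.1.4 says: "For unsolicited non-serious AEs, missing intensities will remain missing and will not be imputed".
- SAP 4.4.1.2.1, on unsolicited non-serious AEs, says: "An observation will be considered an event if it has at least a verbatim term and is not a Grade 0 intensity event".

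**The concern.** The SOC/PT rule names SAEs as countable and then sets a condition that the plan gives no stated means for an SAE to meet. For non-serious AEs, it is stricter than the SAP's own definition of an event. A record with a term and a missing grade is an event under 4.4.1.2.1, yet it does not reach Grade 1 under 4.4.1.5.6.

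The SOC/PT table is the one in this section that shows which events, by MedDRA term, ended participation. Whether an SAE led to early termination is a stated safety endpoint. If the condition is programmed as grade greater than or equal to 1, records with no grade drop out without notice, and a reader comparing the three tables would find subjects with no matching event.

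**Working it through.** No arithmetic applies: the documents give no rate of discontinuation due to AEs and no frequency of missing grades. The check sets the provisions side by side and applies the three rules by hand.

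**Where intensity is specified**

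- Solicited reactions: daily and maximum intensity are derived (SAP 4.4.1.1.1 and 4.4.1.1.2). Presence means Grade 1, 2 or 3, and a missing intensity gives a missing presence (4.4.1.1.3).
- Unsolicited non-serious AEs: intensity is recorded (4.3.2.3.3) and derived, with Missing as an allowed value (4.4.1.2.2).
- Unsolicited AEs and MAAEs: intensity is listed in their rows of Table 5.2.
- SAEs: no intensity appears in the endpoint (Protocol 9.3.2.2, SAP 4.3.2.2), the collection section (SAP 4.3.2.3.4), the derivations (4.4.1.3, which cover last vaccination, onset and duration) or the SAE row of Table 5.2. That row does list study discontinuation.

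**Applying the rules of 4.4.1.5.6 literally** (every event flagged as leading to termination and within the period)

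| Case | Disposition | Overview | SOC/PT |
|---|---|---|---|
| SAE without a grade; termination reason is SAE | counted | counted, through the reason | not counted |
| Non-serious unsolicited AE, grade missing; reason is other AE | counted | counted, through the reason | not counted |
| SAE without a grade; a non-AE reason is checked | not counted | not counted | not counted |
| Solicited reaction of Grade 1 or above; reason is other AE | counted | counted | counted |

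The first two rows are the gap. The third should be rare. Protocol 5.2.9 has safety-related voluntary withdrawals recorded as SAE or other AE, and Protocol 5.2.11 has the most significant reason checked, with SAE ranked first.

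**Comparison with other missing-data conventions**

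Missing causality is taken as related (SAP 5.3.1.2). Unsolicited AEs and SAEs with a missing time of onset stay in the analysis (4.4.1.2.4, 4.4.1.3.2, 5.3.1.5). Those rules keep an incompletely recorded event in the safety tables, whereas the grade condition removes it.

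**The case against.** The strongest reply is that the literal reading defeats the rule's own text. The SOC/PT bullet names SAEs among the event types and again among the flags, which would serve no purpose if no SAE could qualify. The likely intent is to drop Grade 0 records, as 4.4.1.2.1 does. That is a fair reading of intent, but it is not written down, and a programmer working from the text would be entitled to code the threshold as stated.

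Second, the absence of an SAE grade is inferred from silence. The CRF and the electronic SAE form are not among the documents. Non-serious unsolicited AEs are defined as unsolicited AEs less SAEs, so the unsolicited AE endpoint, which includes intensity, can be read to cover serious events up to Visit 2. A solicited reaction can have inpatient hospitalization as its action taken, and it carries a grade. This stands: some or all SAEs may in fact be graded. A reader might infer that every SAE leading to termination is lost, and the documents do not show that.

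Third, a reader might infer that serious outcomes disappear from reporting. They do not. Subjects with an AE termination reason are counted in the disposition and overview tables, and Table 5.2 separately calls for MedDRA terms and study discontinuation for SAEs. This stands too, and limits the point to one tabulation.

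Fourth, SAP 5.3.1.4 on missing intensities is confined to unsolicited non-serious AEs. It supports the point about those events and says nothing about SAEs.

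Finally, the overview counts subjects and the SOC/PT table counts events, so the two need not agree exactly. That explains some differences, but not a subject counted as discontinued for an AE with no corresponding event.

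**Conclusion.** The point holds as a defect in one counting rule. Followed as written, SAP 4.4.1.5.6 leaves out of the SOC/PT table any SAE without a grade, and any unsolicited non-serious AE with a missing grade, that led to termination. The disposition and overview tables still count those subjects through the termination reason.

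The two parts differ in strength. The part on non-serious AEs follows from the SAP text alone. The part on SAEs also assumes that at least some SAEs reach the database without a grade, which the plan's silence suggests but the CRF would have to confirm.

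The number of affected events cannot be computed from the documents. The table is descriptive, no hypothesis is tested on it, and no immunogenicity result changes.

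**What to change.** In the SOC/PT bullet of SAP 4.4.1.5.6, and in the flagged-event arm of the safety overview bullet, state the grade condition by event type:

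- Solicited reactions: keep the threshold of at least Grade 1, which agrees with the presence rule in 4.4.1.1.3. Relaxing it here would count reactions whose presence the SAP treats as missing.
- Unsolicited non-serious AEs: count the event if it is not Grade 0, including when the grade is missing, in line with 4.4.1.2.1.
- SAEs: state that the grade condition does not apply.

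The time-period condition stays as it is. A check that each subject with an AE termination reason has a matching event in the SOC/PT table, or a documented explanation, would expose any remaining gap.

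The cost is one sentence of SAP text and one programming condition, with no change to data collection.
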